APPENDIX 2: DEFINITION OF SUSPECT AND CONFIRMED CASE OF PAS:

1. DEFINITION OF SUSPECT CASE OF PAS BY ULTRASOUND:

Presence of any of the following ultrasound findings:

- 1.1 Loss of the retroplacental hypoechoic line: Loss or irregularity of the hypoechoic plane between the myometrium and the placental border "Clear Zone".
- 1.2 Presence of abnormal placental lagoons: Presence of numerous lagoons including some long and irregular or with presence of turbulent flow.
- 1.3 Bladder wall disruption: Loss or disruption of the bladder wall (hyper echoic band or line between the uterine serosa and the bladder lumen).
- 1.4 Myometrial thinning: Myometrial thinning <1mm or undetectable.
- 1.5 Placental bulge: Deviation of the serosa from the expected plane, caused by an abnormal bulge of placental tissue to neighboring organs, typically the bladder. The uterine serosa appears intact, but its contour is irregular.
- 1.6 Focal exophytic mass: Placental tissue that surpasses the uterine serosa and extends beyond it, often seen within the full bladder.
- 1.7 Uterus-vesical hypervascularization: large amount of Doppler signal between the myometrium and the posterior bladder wall, this sign probably indicates numerous tortuous vessels in this region.
- 1.8 Subplacental hypervascularization: large amount of Doppler signal in the placental bed.
- 1.9 Bridging vessels: vessels that apparently extend from the placenta and cross the myometrium and beyond the serosa to the bladder or other organs.
- 1.10 Vessels that feed the placental lagoons: vessels with high flow velocity that feed the placental lagoons causing turbulence at their entrance.
- 1.11 3D intraplacental hypervascularization: abnormal placental vessels, with tortuous courses and various gauges.

2. DEFINITION OF SUSPECT CASE OF PAS BY MAGNETIC RESONANCE:

Presence of any of the following ultrasound findings:

2.1 Hypointense bands in T2: One or more areas of hypo intensity in T2, usually with a linear configuration and in contact with the maternal surface of the placenta.

2.2 Placental bulging: Deviation of the uterine serosa from the expected plane, caused by abnormal bulging of placental tissue to adjacent organs.

2.3 Loss of the hypointense interface in T2: loss of the dark line behind the placental bed in T2 images.

2.4 Myometrial thinning: Thinning of the myometrium that covers the placenta less than 1mm or even invisible.

2.5 Bladder wall disruption: Hypointense bladder wall irregularity or disruption, which may be accompanied by blood products in the bladder lumen.

2.6 Focal exophytic mass: Placental tissue that surpasses the uterine serosa and extends beyond it, frequently seen within the full bladder and lateral to the parametrium.

2.7 Abnormal vascularization of the placental bed: prominent vessels in the placental bed with disruption of the uteroplacental interface, can extend to the myometrium to a variable degree, reaching the uterine serosa and can be accompanied by extensive neovascularization around the bladder, uterus and the vagina.

2.8 Placental heterogeneity: Heterogeneous signals in the placenta that can be seen on T1 and T2.

2.9 Asymmetric thinning of the placenta: Part of the placenta, the portion that is involved with PAS and usually the part that covers the internal cervical os (in cases of placenta previa) are asymmetrically thinned compared to the rest of the placental tissue . 2.10 Placental ischemic infarction: In the acute phase, areas of hyperintensity in T2 and

hypo intensity in T1 are present, areas of placental asymmetry are described in chronic infarcts.

2.11 Abnormal intraplacental vascularization: Abnormal, tortuous and elongated vessels in T2 deep in the placenta.

3. DEFINITION OF PAS CONFIRMED CASE:

Confirmed case in Placenta Acreta laparotomy: The patient meets any of the following criteria:

- No placental separation with the administration of oxytocin and controlled cord traction.

- Attempts to remove the placenta result in heavy bleeding from the placental bed.

- Macroscopically, the uterus does not show an obvious placental bulge, no placental tissue is seen invading the surface of the uterus, and there is minimal or no neovascularization.

Confirmed case in laparotomy of Placenta increta: The patient meets any of the following criteria:

- Abnormal macroscopic findings in the placental bed, bluish or purplish color, presence of placental bulge.

- Increased Hypervascularization (Multiple vessels run parallel craniocaudal in the uterine serosa)

- No placental tissue is observed invading through the uterine serosa.

- Cord traction results in outward uterine traction without achieving placental separation.

Confirmed case in Placenta Percreta laparotomy: The patient meets any of the following criteria:

Placenta percreta grade 3A: Limited to the serosa:

- Abnormal macroscopic findings on the surface of the uterine serosa, the placental tissue invades through the surface of the uterus.

- It does not invade any organs, including the posterior bladder wall (there is a clear surgical plane between the uterus and the bladder)

Placenta percreta grade 3B: With invasion of the bladder wall:

- There are placental vessels that invade the bladder surface but not other organs.

- A clear plane between the bladder and the uterus cannot be identified

Placenta percreta grade 3C: With invasion of other pelvic organs:

- Placental vessels invade the round ligament, vaginal wall, lateral pelvic walls, or other pelvic organ (with or without invasion of the bladder)

APPENDIX 3

Inclusion and exclusion format Institution: ______ Clinic history: _____ Screening number:

Inclusion and exclusion criteria

	Inclusion criteria	Yes	No
1	Pregnant woman over 18 years of age		
2	History of previous cesarean section and previous placenta		
	previa		
3	Prenatal ultrasound or magnetic resonance diagnosis of PAS.		
	(Appendix 2, Suspected case of PAS) regardless of the		
	suspected degree of severity of the disease.		
4	Requirement for surgical management of placental accreta on a		
	scheduled basis.		
5	Patients without active vaginal bleeding in the period		
	immediately prior to surgery (Patients entering the operating		
	room without active bleeding).		

	Exclusion criteria	Si	No
1	Woman without children or newborns		

Flogible patient	Si	No
Elegiole patient		

Appendix 4

Screening summary Institution:

		7					
	Identification					oation	Not
	Date	Age	Name	ID	If	If	participating
					Patient	Patient	causes
					is	is not	(number
					elegible	elegible	according to
					Asigned	Asigned	list)
					numer	numer	
					(Group	(Group	
					186)	189)	
1							
2							
3							
4							
5							
6							
7							
8							

Not partipating causes				
1 Some exclusion criteria				
2	Denial of consent			

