Women with a previous cesarean section, anterior placenta previa, and imaging (ultrasound or MRI) with signs suggestive of PAS will be eligible to participate (See Appendix 2: Definition of a suspected PAS case). Informed consent will be requested from these patients prior to surgery. Considering that these are pregnant women, the participation of the husband or spouse will be included in the informed consent (Appendix 7). In the event that the patient does not have a husband or spouse, the "Declaration of mother head of the family" will be filled out (Appendix 8).

Randomization will be carried out before starting the surgical procedure, with the aim of reducing the possibility of selection bias by the surgical team since there is no blinding.

It is possible that some patients who are eligible before surgery and who have signed the informed consent, will cease to be eligible if macroscopic signs suggestive of PAS are not found at laparotomy (See Appendix 2: Definition of confirmed PAS case) (that is, if present a false positive result of the prenatal diagnostic images), which has been described in up to 22.6%¹¹ of the cases. These patients will be considered screening failures in the recruitment process and will be excluded from the statistical analysis.

9.5.1. Inclusion criteria:

- Pregnant women over 18 years of age.
- History of previous cesarean section and anterior placenta previa
- Patients with prenatal diagnosis by ultrasound or MRI of PAS (See Appendix
 2: Definition of a suspected case of PAS), regardless of the suspected degree of severity of the disease.
- Requirement for surgical management of placental accreta on a scheduled basis.
- Patients without active vaginal bleeding in the period immediately before surgery (Patients entering the operating room without active bleeding).

9.5.2. Exclusion Criteria:

- Women without previous living children.

9.6. Sample size:

As the aim of the study is not to compare the effectiveness between interventions, a formal power calculation was not performed. A sample size of 60 participants. According to the estimated recruitment rate for each center, the following distribution is proposed: 36 patients from Indonesia, 12 patients from Argentina and 12 patients from Colombia to address the feasibility objectives.

9.7. Recruitment strategy:

9.7.1. Participant selection:

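### Appendix 2 confirms PAS on any single criterion, including absent signs, and so contradicts the exclusion rule that sets screening failure and the analysis set

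*Combined protocol and SAP*

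**What the plan says.** Appendix 2, section 3 defines a confirmed case separately for accreta, increta and percreta. The accreta rule reads "Confirmed case in Placenta Acreta laparotomy: The patient meets any of the following criteria", and increta has the same rule. The third accreta criterion begins "Macroscopically, the uterus does not show an obvious placental bulge, no placental tissue is seen invading the surface of the uterus" and continues with little or no neovascularization. The third increta criterion is "No placental tissue is observed invading through the uterine serosa".

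The body of the protocol works in the other direction:

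- **9.4:** a consented woman "will cease to be eligible if macroscopic signs suggestive of PAS are not found at laparotomy". She is then a screening failure and is left out of the statistical analysis.
- **9.7.1:** the surgeon looks for macroscopic signs on the anterior face of the uterus. If PAS is not confirmed, she is a screening failure.
- **9.11:** she is excluded if the Appendix 2 criteria are not present.
- **Appendix 5, items 8a to 8c:** the signs are sought on the anterior surface before the uterus is opened, using the Appendix 2 list. Women in whom signs are ruled out are excluded.

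Appendices 10 and 11 agree on the order: findings are identified at step 5 and hysterotomy is step 7. Section 8.1 makes screening failure percentage a primary endpoint.

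**The concern.** There are two contradictions.

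First, the same surface appearance, with no bulge, no tissue on the surface and no notable vessels, is a confirming criterion in Appendix 2 and the ground for exclusion in 9.7.1 and Appendix 5.

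Second, Appendix 5 item 8a sends the surgeon to Appendix 2 for signs to be judged before hysterotomy, but the positive accreta criteria listed there can only be observed later. Section 2 says 64.6% of PAS cases are accreta, and the FIGO variable in section 15 provides for Grade 1, so accreta is plainly meant to be in the trial.

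One definition thus controls a primary endpoint and the denominator of every clinical table. Three centres could each follow the protocol and classify the same woman differently. Section 3 gives the purpose of the study as informing a definitive trial, and a screening failure rate without a fixed meaning does not serve that purpose.

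**Working it through.** **The criteria, sorted by type and by when they can be assessed**

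| Appendix 2 criterion | Type | Assessable before hysterotomy? |
|---|---|---|
| Accreta 1: "No placental separation with the administration of oxytocin and controlled cord traction" | positive | no, needs attempted separation |
| Accreta 2: "Attempts to remove the placenta result in heavy bleeding from the placental bed" | positive | no, needs attempted removal |
| Accreta 3: surface not remarkable | absent sign | yes |
| Increta 1 and 2: colour change, bulge, increased vessels | positive | yes |
| Increta 3: no tissue through the serosa | absent sign | yes |
| Increta 4: "Cord traction results in outward uterine traction without achieving placental separation" | positive | no, needs cord traction |
| Percreta 3A, 1: tissue through the surface | positive | yes |
| Percreta 3A, 2: no organ invaded, clear plane | absent sign | yes |

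**Can the literal rule exclude anyone?** Take four surface signs (bulge, tissue through the serosa, neovascularization, colour change), each present or absent: 2^4 = 16 patterns. The 8 without tissue through the serosa all meet increta 3. The 8 with it meet percreta 3A, 1. So 8 + 8 = 16 are confirmed and 0 are ruled out. Whether the single-criterion rule also reaches percreta 3A, 2 makes no difference.

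**Does reading the criteria jointly help?** If all criteria of a grade were required, the absent signs would do no harm. But accreta 1 and 2 and increta 4 come after hysterotomy, so neither accreta nor increta could then be confirmed at the item 8a decision point.

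**Size.** Inputs, all from 9.4 and 9.6: a false-positive share of up to 22.6%, and 60 participants split 36, 12 and 12 (36 + 12 + 12 = 60, which agrees with the plan). There is no power calculation to reproduce.

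- Literal rule: 0 of 60, or 0%.
- Plan's figure: 60 × 0.226 = 13.6 screening failures. By centre: 36 × 0.226 = 8.1 and 12 × 0.226 = 2.7 at each of the other two.
- If 60 counts randomised women, the analysed set is 60 under the literal rule or 60 − 13.6 = 46.4 under the plan's figure.
- If 60 counts confirmed women, the number to randomise is 60 or 60 / (1 − 0.226) = 77.5, so 78.
- One woman classified the other way moves the percentage by 1/60 = 1.7 points overall, 1/36 = 2.8 points at the largest centre and 1/12 = 8.3 points at a centre of 12. The denominators 60, 36 and 12 are assumed.

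Requiring a positive surface sign could push screening failure above 22.6%. The excess cannot be computed, because the documents do not give the share of accreta cases with visible signs.

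**The case against.** The strongest reply is that the intent is clear. Sections 9.4, 9.7.1 and 9.11 and Appendix 5 all run the same way: signs found, continue; signs not found, exclude. The single-criterion phrase may be a drafting slip. Appendix 2 shows another, since its MRI list is headed as ultrasound findings. Surgeons will probably read the criteria as joint descriptions of each grade. That is plausible, but a joint reading does not cure the timing problem, and 9.11 and item 8a both rely on Appendix 2 as written.

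Other points limit the size of the problem:

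- The decision is about PAS, not accreta. A woman with colour change or increased vessels meets a positive increta criterion whatever her final grade, so the timing conflict touches only women with no surface sign. This stands; their number is unknown, and the 64.6% does not supply it.
- Accreta 3 tolerates minimal neovascularization, so it is not purely a list of absences. True, but a normal uterus still meets it.
- The pre-hysterotomy timing is explicit only in item 8a. Section 9.4 says at laparotomy, and section 15 says only that PAS is ruled out intraoperatively. The looser wording adds to the ambiguity.
- Non-separation of the placenta is said to confirm PAS in the hysterectomy technique (9.11, Appendix 5), and spontaneous delivery is recorded in both arms at step 9b of Appendices 10 and 11. Both come after the decision point, and nothing says they revise study status.
- Safeguards exist: supervision by the coordinator, video and photographs as quality control, histology, blinded expert review (11.2), and a surgical note with findings, FIGO grade and presence of PAS. They allow partial reconstruction, but no section uses them to set the endpoint or the analysis set.
- The analyses are descriptive and no screening failure threshold is stated. That softens the consequence, but a descriptive percentage still needs a defined numerator.

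**Conclusion.** The concern holds and must be fixed. Appendix 2 as written cannot produce the screening failure that the protocol body defines. For accreta it also offers no positive criterion that can be assessed at the stated decision point. The readings differ by up to 22.6 percentage points, the gap between the literal 0% and the maximum false-positive share cited in 9.4, or up to about 14 of 60 women.

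That gap is between two readings of the text and does not predict what centres will do. It assumes that the cited share applies to this population and that 60 is the denominator. The actual number of women who would be classified inconsistently is not known. That exclusion follows disclosure of the allocation is a separate matter, and this conclusion does not rest on it.

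**What to change.** Reconcile Appendix 2, section 3 with 9.4, 9.7.1, 9.11 and Appendix 5 item 8. One definition, assessable at the stated decision point, should set screening failure and the analysis set in all centres and both arms. The choice of signs and time point belongs to the investigators and is not proposed here.

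Three smaller additions:

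1. State whether the hysterectomy-arm sentence on non-separation of the placenta affects study status.
2. Record in the CRF which Appendix 2 criterion was relied on and when it was assessed.
3. Report screening failure by site and by arm. The institution and randomization arm are already collected.

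The cost is amendment wording in those five places and up to two CRF fields. Whether any operative step changes depends on the investigators' choice.

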Control	Patients with a confirmed diagnosis of PAD (See Annex 2, Definition of a confirmed case of PAD). Hysterectomy.					
Population	Pregnant women with a prenatal ultrasound or MRI diagnosis of PAD (See Appendix 2: Definition of suspected case of PAD), who will be taken to surgery to treat this disease.					
Inclusion Criteria	 Pregnant woman older than 18 years. History of previous cesarean section and previous placenta previa. Prenatal diagnosis by ultrasound or MRI of PAS (See Appendix 2: Definition of suspected case of PAS), regardless of the suspected degree of severity of the disease. Requirement of surgical management of placental accreta on a scheduled basis. Patients without active vaginal bleeding in the period immediately prior to surgery (Patients admitted to the operating room without active bleeding). 					
Exclusion Criteria	Women without previous living children.					
Sample Size	60 participants					
Randomization method	Permuted blocks of 4 and 6, stratified by center					
Primary outcomes:	 Proportion of eligible patients who agree to participate in the study. Percentage of screening failure. Percentage of patients assigned to each arm of the study. Percentage of patients with cross over between assigned arms of the study. Number of subjects completing follow-up at 42 days postpartum. 					

Secondary outcomes:	- Maternal death					
	- Intraoperative bleeding volume measured in mL.					
	- Blood component transfusion requirement, median transfusion of red blood cell units (RBCs), platelets, fresh frozen plasma, cryoprecipitate and fibrinogen.					
	- Compliance with at least one WHO Near Miss criterion (See Appendix 1).					
	- Ureteral lesions.					
	- Bladder lesions					
	- Need for surgical reintervention.					
	- Days of hospital stay in Intensive Care Unit.					
	- Days of general and postoperative hospital stay.					
	- Use of uterine tamponade with hydrostatic balloons.					
	- Presence of supra fascial hematoma.					
	- Presence of postoperative ileus.					
	- Vital status of the newborn.					
	- Weight of the newborn.					

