Women with a previous cesarean section, anterior placenta previa, signs of PAS on ultrasound or prenatal magnetic resonance imaging (See Appendix 2: Suspicious case of

PAS) and who meet the inclusion criteria will be considered as possible candidates to participate in the study. Patients will be identified by the medical group and evaluated for their eligibility at the time of hospital admission before surgery.

Once the treating medical personnel confirm the eligibility of the patient, she will be provided with complete information about the study and the physical informed consent, the patient will have at least 48 hours to evaluate it, discuss it and decide whether or not she wishes to participate.

Participants who voluntarily decide to take part in the study will not receive any payment or remuneration as a result of their participation.

Some anonymized data of the women who decline their participation in the study and that will be used in the CONSORT report will include:

Date of cesarean section. Ethnicity Number of living children Reason why the patient is not eligible, or if she is eligible because she declined to participate.

Before the start of the surgical procedure, the clinical coordinator of the study will be in charge of revealing the surgical intervention to which the patient has been randomized to reduce the probability of selection bias since blinding is not possible in this study.

Once the laparotomy has been performed, the surgeon will define whether or not there are macroscopic signs on the anterior face of the uterus that confirm the diagnosis of PAS (See Appendix 2, Confirmed case of PAS). The clinical diagnostic criteria reported by the International Federation of Gynecology and Obstetrics (FIGO) will be used¹⁷.

At that time, if the diagnosis of PAS is confirmed, the randomized intervention will continue. If the diagnosis of PAS is not confirmed, the patient will be considered a screening failure.

The entire process from the disclosure of the randomization, the confirmation or exclusion of PAS and the performance of the randomized intervention will be supervised by the study coordinator in each hospital.

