Additionally, as a quality control, all surgery will be recorded on video and photos. With special emphasis on intraoperative findings after laparotomy that confirm or rule out the diagnosis of PAS and define the continuity of the patient in the study, or the exclusion of it (in case PAS is ruled out). The photographic and video recording of the findings during laparotomy should account for the presence of the clinical criteria for PAS endorsed by FIGO¹⁷ (See Appendix 10).

Additionally, a photo and video record will be taken of the prenatal ultrasound that suggests a diagnosis of PAS (according to the medical criteria of the investigator), as well as photos of the histological study that confirm or rule out the diagnosis of PAS. Those patients who meet all the inclusion criteria and all the exclusion criteria are discarded will finally be chosen for the study (See Appendix 2: Inclusion / Exclusion Form). Each center will be responsible for completing the information of all the participants who were not entered into the study, recording the reasons for their NOT inclusion (See Appendix 3: Summary Screening).

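### The placenta criterion reads *previous* in the synopsis and the Appendix 3 form but *anterior* in sections 9.4, 9.5.1 and 9.7.1, and the form's exclusion item departs from section 9.5.2

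*Combined protocol and SAP*

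**What the plan says.** Three places in the protocol body give the placenta criterion as a location. Section 9.5.1 lists "History of previous cesarean section and anterior placenta previa". Section 9.4 states "Women with a previous cesarean section, anterior placenta previa, and imaging (ultrasound or MRI) with signs suggestive of PAS will be eligible to participate", and section 9.7.1 opens in the same way: "Women with a previous cesarean section, anterior placenta previa, signs of PAS on ultrasound or prenatal magnetic resonance imaging".

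Two places give it as history. The synopsis lists "History of previous cesarean section and previous placenta previa", and item 2 of the form in Appendix 3 reads "History of previous cesarean section and previous placenta", with the word *previa* on the next line of the table.

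For the exclusion, section 9.5.2 and the synopsis both say "Women without previous living children". The form says "Woman without children or newborns".

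The form is a yes/no sheet that ends in a box for whether the patient is eligible. Section 9.7.1 ties the final choice of patients to it: "Those patients who meet all the inclusion criteria and all the exclusion criteria are discarded will finally be chosen for the study". That sentence cites the form as Appendix 2, although it is printed as Appendix 3. The next sentence cites the screening summary as Appendix 3, although it is printed as Appendix 4.

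**The concern.** A previa in an earlier pregnancy and an anterior previa in this one are different facts about a woman. Neither implies the other. The conflict reaches the sheet on which each screened woman is marked eligible or not, so it is not confined to background text.

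The first primary endpoint in section 8.1 is the proportion of eligible women who agree to participate. A feasibility study exists largely to estimate that proportion and the flow of candidates for a definitive trial. If centres apply different versions of one criterion, their counts of eligible women do not measure the same thing and cannot be pooled cleanly.

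Location also matters to the design. Section 2 describes partial resection as feasible when the disease affects the anterior wall. Section 9.7.1 and Appendix 5 have the surgeon confirm the diagnosis from signs on the anterior face of the uterus.

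**Working it through.** The documents contain no figure to reproduce: section 9.6 reports no power calculation, and the point depends on none. The check is a comparison of wording.

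| Place | Placenta criterion | Exclusion |
|---|---|---|
| Synopsis | previous | no previous living children |
| Section 9.4 | anterior | not stated |
| Sections 9.5.1 and 9.5.2 | anterior | no previous living children |
| Section 9.7.1 | anterior | not stated |
| Appendix 3 form | previous | no children or newborns |

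The other four inclusion items on the form match section 9.5.1 in substance.

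**Placenta item.** Take women who meet every other criterion and classify them on the two facts.

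| Group | Anterior previa now | Previa in an earlier pregnancy | Section 9.5.1 | Form, read literally |
|---|---|---|---|---|
| A | yes | no | eligible | not eligible |
| B | yes | yes | eligible | eligible |
| C | no | yes | not eligible | eligible |
| D | no | no | not eligible | not eligible |

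The two readings agree on groups B and D and disagree on A and C. Form item 3 does not fill the gap. It accepts any one imaging sign from Appendix 2, and several of those signs, such as loss of the clear zone or T2 hypointense bands, are not tied to the anterior wall.

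**Primary endpoint.** Let A, B and C also stand for the group sizes, and let p with the matching subscript be the share of each group that would agree.

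- Under section 9.5.1: (A·p_A + B·p_B) / (A + B)
- Under the literal form: (B·p_B + C·p_C) / (B + C)

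The denominator moves from A + B to B + C, a change of C − A. The proportion itself stays the same if willingness is equal in all three groups, and otherwise it can move either way. The documents give none of these quantities, so neither shift can be computed.

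**Screening failure.** Section 15 counts women with suspected disease who agreed and in whom it was ruled out during surgery. It is not defined on the eligible count. The form's wording would reach it only by changing who consents and comes to laparotomy.

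**Exclusion item.** Every candidate has had a cesarean section, so few can be without any child in the plain sense. The two wordings part mainly for a woman whose earlier children have all died: section 9.5.2 excludes her, and the form may not. The form's mention of newborns has no clear meaning.

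**The case against.** The best reply is that this is a translation slip that no clinician would follow. The Introduction makes the reverse swap, describing an earlier cesarean delivery as *anterior*. Spanish remains in the visit headings of section 9.10, in some definitions in section 15, and in the answer columns of this very form. Section 9.7.1 has the treating team confirm eligibility, and Appendix 5 gives the assessment to principal investigators who also helped design the protocol. They are unlikely to turn away a woman because her previa is her first.

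Much of this stands, and it limits what may be inferred.

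- A reader might infer that the form does select a different population. That holds only on the literal reading. The source-language form is not in the documents, and nothing shows that the literal reading was used.
- A reader might see the form in conflict with the protocol as a whole. The synopsis shares the form's placenta wording, so on that item the split runs inside the protocol.
- A reader might infer that women without an anterior placenta reach the analysis. Appendix 5 requires signs on the anterior surface before hysterotomy and excludes women in whom they are ruled out, which limits this. The allocation has been revealed by then, so such women would count as screening failures after randomization.
- A reader might count two primary endpoints as corrupted. Only one is worded on eligible women.
- A reader might attach the problem to the 36 of 60 patients planned in Indonesia. No section says in which language any centre uses the form.

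The reply does not dispose of the point. Section 9.5.1 uses *previous* and *anterior* in one phrase with different meanings, so a reader has no cause to treat them as synonyms. Monitoring under section 10.3 and Appendix 5 compares entered data with clinical records, and so would not detect a form that differs from section 9.5.1.

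**Conclusion.** The contradiction is real and sits in operative eligibility text: synopsis and Appendix 3 against sections 9.4, 9.5.1 and 9.7.1 for the placenta, and Appendix 3 against section 9.5.2 and the synopsis for the exclusion. It should be corrected.

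The harm is conditional. If the form is followed as printed, women with a first previa who meet section 9.5.1 are marked ineligible, the form checks no placental location, and the denominator of one primary endpoint changes. Screening failure is touched only through enrolment. The exclusion mismatch is the smaller part and probably concerns few women. The size of either effect cannot be derived from the documents. That the cause is translation is an inference, though a likely one.

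**What to change.** 1. Reconcile the passages, then make the synopsis and the Appendix 3 form repeat the reconciled criteria of sections 9.5.1 and 9.5.2 word for word. State that the placental location refers to the current pregnancy. Section 9.5.1 does not say so, and its opening words could be read as making this a history item too.
2. In section 9.7.1, cite the form as Appendix 3. Correct the neighbouring citation of the screening summary to Appendix 4 at the same time.
3. Reissue the form to the three centres.
4. Check from the existing screening logs whether any woman was refused or admitted on the literal wording. The Appendix 4 log codes only an exclusion criterion or refusal of consent, so the completed Appendix 3 forms will be needed to find women whose only *No* was on item 2.

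The cost is a few words in two places, two citations, one amendment submission (Appendix 5 requires this for changes to the protocol or its appendices) and one pass through the screening records. No change to sample size or analysis is needed.
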